## **6.2 Administration**

Subjects randomized to the intervention group will undertake first usage of the range of dental/denture products under supervision at the clinical site. These subjects will be instructed to self-administer their assigned range of products twice per day (morning and evening) per the [Product Usage Instructions](#) provided to the subject and will use their products under supervision again at Visit 3 to ensure adherence to the product usage instructions.

### **6.2.1 Medication/Dosing Errors**

Medication/dosing errors may result, in this study, from the administration or consumption of:

- the wrong product,
- by the wrong subject,
- at the wrong time,

Property of GSK Consumer Healthcare - Confidential

May not be used, divulged, published or otherwise disclosed without the consent of GSKCH

SP1963/SOP-208661: Template Version: 14 Mar 2019

- or at the wrong dosage.

Such medication/dosing errors occurring to a study subject are to be captured in the CRF. In the event of medication dosing error, the sponsor should be notified **immediately and under no circumstance should this exceed 24 hours**.

Medication/dosing errors are reportable irrespective of the presence of an associated AE, including:

- Medication/dosing errors involving subject exposure to any of the study products;
- Potential medication/dosing errors or uses outside of what is foreseen in the protocol that do or do not involve the participating subject.

If a medication/dosing error is accompanied by an AE, as determined by the investigator, the medication/dosing error and, any associated adverse event(s) are to be captured in the CRF AE form.

### 6.2.2 Overdose

An overdose is a deliberate or inadvertent administration of a product at an amount higher than specified in the protocol.

Overdose per se is not an AE. However, any clinical sequelae of an overdose should be reported as an AE (and serious adverse event (SAE), if appropriate). For reporting, follow the AE and SAE reporting instructions.

### 6.3 Investigational/Study Product Storage

The investigator, or designee, will ensure that all study products are stored in a secured area with controlled access under required storage conditions and in accordance with applicable regulatory requirements and the product label.

Site systems must be capable of measuring and documenting (for example, via a log), at a minimum, daily minimum and maximum temperatures for all site storage locations (as applicable, including frozen, refrigerated, and/or room-temperature products). This should be captured from the time of first product receipt throughout the study. Even for continuous monitoring systems, a log or site procedure that ensures active daily evaluation for excursions should be available. The operation of the temperature-monitoring device and storage unit (for example, refrigerator), as applicable, should be regularly inspected to ensure it is maintained in working order.

Any excursions from the product-label storage conditions should be reported to appropriate site staff upon discovery and communicated to sponsor as soon as possible. The site should actively pursue options for returning the product to the storage conditions as described in the labeling, as soon as possible. Excursions from the storage requirements, including any actions taken, must be documented as a protocol deviation and reported to the Sponsor.

Once an excursion is identified, the affected product (or products) must be quarantined and not used until the sponsor provides documentation of permission to use. Use of any of the affected product(s) prior to sponsor approval will be considered a protocol deviation.

Site staff will instruct subjects on the proper storage requirements for all take-home products.

## 6.4     **Investigational/Study Product Accountability**

All products supplied are for use only in this clinical study and should not be used for any other purpose.

All study products must be received by a designated person at the study sites, handled and stored safely and properly, and kept in a secured location to which only the staff have access. Upon receipt, all study products should be stored according to the instructions specified on the product labels. Study products are to be dispensed only to subjects enrolled in the study in accordance with the protocol, by authorized site staff.

The investigative site must maintain adequate records documenting the receipt, use, loss, or other disposition of all the product supplies. All study products will be accounted for using the investigational/study product accountability form/record. The investigator is responsible for study product accountability, reconciliation, and record maintenance.

The accountability records must be available for inspection by the study monitor during the study. Monitoring of product accountability will be performed by the monitor during site visits and at the completion of the study.

All unused product should be returned to the study site by the subjects at each visit.

### 6.4.1    **Destruction of Investigational/Study Product Supplies**

At the end of the study, the Principal Investigator or an appropriate designee, and a representative of GSK CH (study monitor) will inventory all used and unused study products and sundry items. The investigational/study product accountability record for returned study products will then be completed. Please see table of sundry items for return or destruction details. Detailed instructions for the return of study product/study supplies for the accountability checks and subsequent destruction will be provided by GSK CH during the study in time for study close out visit.

## 6.5     **Blinding and Allocation/Randomization**

All subjects will be centrally randomized to one of the study arms using an Interactive Response Technology (IRT). Before the study is initiated, training, login information and directions for the IRT will be provided. Study products will be dispensed according to the instruction received through the IRT at the appropriate study visits.

Returned study products should not be re-dispensed to any subject.

The investigator's knowledge of the product allocation should not influence the decision to enroll a subject or affect the order in which subjects are enrolled.

This study is described as single-blind (to the examiner(s) performing the plaque and gingivitis assessments).

To ensure the examiner remains blinded throughout the study, staff involved in the dispensing of study products will work in a separate area. The examiner is not permitted in any area where study product is stored, dispensed, or in use.

Subjects will be instructed not to remove study products from the opaque bags provided, outside of the dispensing room, while at the study site. Subjects randomized to the interventional group will have the study products, sundry items and their diary and usage instructions contained

Property of GSK Consumer Healthcare - Confidential

May not be used, divulged, published or otherwise disclosed without the consent of GSKCH

SP1963/SOP-208661: Template Version: 14 Mar 2019

within the bag, whilst the subjects randomized to the no intervention group will have their diary in the bag.

Dispensing staff will not be involved in any efficacy/safety assessment procedures during the study.

## 6.6 Breaking the Blind

At the initiation of the study, the study site will be instructed on the method for breaking the blind. The method will be an electronic process.

The electronic system will be programmed with blind-breaking instructions. In case of an emergency, the investigator has the sole responsibility for determining if unblinding of a subject's product assignment is warranted. Subject safety must always be the first consideration in making such a determination. If the investigator decides that unblinding is warranted, the investigator should make every effort to contact the Sponsor prior to unblinding a subject's product assignment unless this could delay emergency treatment of the subject.

If a subject's product assignment is unblinded, the Sponsor must be notified within 24 hours after breaking the blind. The date and reason that the blind was broken must be recorded in the source documentation and case report form, as applicable.

Any AE or incident associated with breaking the blind must be recorded and reported as specified in this protocol. The study site may also be required to inform the Institutional Review Board / Ethics Committee (IRB/EC) if the blind is broken.

## 6.7 Compliance

A diary will be supplied to promote compliance and to capture details of product use throughout the study period. Subjects randomized to the no intervention group should record their dental/denture cleansing events in the diary. All subjects should also record, in the diary, additional information such as AEs or changes in medications used. Any additional details relevant to efficacy or safety should be reviewed by the investigator (or suitably qualified designee) with the subjects and transcribed to the CRF as appropriate. Additionally, all subjects currently active in the study will receive an SMS (text message) reminder from the study site prior to a scheduled visit (Visits 2-4) to remind them of the requirement for no oral hygiene on the morning prior to their visit.

During study site visits (Visits 2&3) subjects randomised to use of the interventional range of products will have correct product usage demonstrated to them by the study site staff. Subjects will then undergo supervised product usage which will be witnessed by the study site staff and incorrect application will be corrected.

Subjects randomised to the interventional range of products will be supplied with a dosing cup to ensure accurate dosing of the mouthrinse. These subjects will also be asked to bring their assigned study products at each visit, so that the compliance assessments can be made based upon observation of the amount of product used and so they can undergo supervised product application at Visit 3.

The number of any missed or additional applications or doses for subjects in the intervention group will be captured as protocol deviations and transcribed from the diary into the CRF. Subjects will be re-instructed in the correct usage requirements and diary completion as needed.

Property of GSK Consumer Healthcare - Confidential

May not be used, divulged, published or otherwise disclosed without the consent of GSKCH

SP1963/SOP-208661: Template Version: 14 Mar 2019

For subjects in the non-intervention group, changes to their oral hygiene behavior compared to their behavior as recorded at screening which are deemed significant and consistent by the investigator or their designee will be captured as protocol deviations in the CRF.

Subjects randomized to use of the interventional range of products will be instructed in/reminded of the correct usage of the product at visits 2 and 3 by the dispensing staff with subsequent supervised product usage at these visits.

Failure of any subject to follow the oral care advice given at Visit 2 (see section 8.2.1) will not be considered as a deviation except where this failure is covered by other inclusion/exclusion criteria, lifestyle considerations or product usage instructions detailed within this protocol.

## **6.8 Concomitant Medication/Treatment(s)**

Any medications, treatments or vaccine (including over-the-counter or prescription medicines, vitamins, and/or herbal supplements) taken during the study, from signing the informed consent, must be recorded in the CRF with indication, reason for use, unit dose, daily dose, and start and stop dates of administration. All subjects will be questioned about concomitant medication/treatments at each site visit.

Details of any relevant dental, medical or surgical history (within the last year), including allergies or drug sensitivity, will be recorded in the CRF. The use of concomitant medications is permitted in this study except for the use of anti-biotics, anti-inflammatory or anti-coagulants drugs as per the exclusion criteria, and any medications that in the opinion of the investigator would interfere with the conduct of this study per the inclusion/ exclusion criteria. Occasional use of anti-inflammatory drugs (e.g. ibuprofen) is allowable, if in the opinion of the investigator, the use would not affect the gingival condition.

Medication/treatments taken within 28 days of signing the informed consent form will be documented as a prior medication/treatment. Medications/treatments taken on and after Visit 2 will be documented as concomitant medication/treatments.

## **7 DISCONTINUATION OF STUDY INTERVENTION AND SUBJECT DISCONTINUATION/WITHDRAWAL**

### **7.1 Subject Discontinuation/Withdrawal**

A subject may withdraw from the study at any time at his or her own request or may be withdrawn at any time at the discretion of the investigator or sponsor for safety, behavioral reasons, or the inability of the subject to comply with the protocol-required schedule of study visits or procedures.

The following circumstances require discontinuation of study product and/or premature subject withdrawal:

- Protocol violation that may impact the subject's safety
- Withdrawal of informed consent
- Subject lost to follow-up
- Unblinding of the subject
- Pregnancy

Property of GSK Consumer Healthcare - Confidential

May not be used, divulged, published or otherwise disclosed without the consent of GSKCH

SP1963/SOP-208661: Template Version: 14 Mar 2019

---

If a subject is discontinued or prematurely withdraws from the study, the reason(s) for discontinuation or withdrawal and the associated date must be documented in the relevant section(s) of the CRF.

## 7.2 Lost to Follow up

If a subject fails to return to the site for a required study visit the site must attempt to contact the subject and reschedule the missed visit as soon as possible and counsel the subject on the importance of maintaining the assigned visit schedule and ascertain whether the subject wishes to and/or should continue in the study.

A subject will be considered lost to follow up if he or she repeatedly fails to return for scheduled visits and is unable to be contacted by the study site. Before a subject is deemed lost to follow up, the investigator or designee must make every effort to regain contact with the subject (where possible, 3 telephone calls and, if necessary, a certified letter to the subject's last known mailing address or local equivalent methods). These contact attempts should be documented. If contact is made with the subject, the investigator should inquire about the reason for withdrawal, request that the subject return all products that they had been dispensed and if appropriate request that the subject return for a final visit and follow-up with the subject regarding any unresolved adverse events (AEs) or incidents.

Final safety assessments may be carried out when the subject returns to the study site, at the investigator's discretion and subject's consent, which could include an OST and OHT examination.

Should the subject continue to be unreachable, he/she will be considered to have withdrawn from the study and lost to follow up.

Lack of completion of all or any of the early termination procedures will not be viewed as protocol deviations so long as the subject's safety was preserved.

If the subject withdraws from the study and withdraws consent for disclosure of future information, no further evaluations should be performed, and no additional data should be collected. The sponsor may retain and continue to use any data collected before such withdrawal of consent.

## 8 STUDY PROCEDURES

This section lists the procedures to be completed at each planned study visit. The timing of each procedure is listed in the Schedule of Activities section.

Adherence to the study design requirements, including all procedures are essential and required for study conduct.

### 8.1 Visit 1/Screening

Screening procedures will be conducted by the Investigator, or suitably qualified designee.

Subjects will be screened within 1-28 days prior to randomization to confirm that they meet the subject selection criteria for the study.

The following Screening procedures will be completed, in the following order (wherever possible), and the findings recorded in the CRF:

Property of GSK Consumer Healthcare - Confidential

May not be used, divulged, published or otherwise disclosed without the consent of GSKCH

SP1963/SOP-208661: Template Version: 14 Mar 2019

1. Informed Consent
2. Demographics
3. Review of medical history (including smoking/tobacco use status) and prior medication/treatment
4. Review of current/concomitant medication
5. Review of dental history
6. Well-fit assessment of the RPD
7. Subject removes RPD
8. Well-made assessment of the RPD
9. Full OST and OHT examinations
10. Gross gingival assessment
11. Review of the inclusion/exclusion criteria
12. Subject eligibility
13. RPD is returned to subject
14. AEs and Incidents recorded

### **8.1.1 Screening Procedures**

#### **8.1.1.1 Informed Consent**

The investigator, or designee, must obtain informed consent from each subject participating in this study after adequate explanation of the aims, methods, objectives, and potential hazards of the study. Two copies of the informed consent form (ICF) will be signed and dated by the subject, the subject will retain one copy and the other will be kept at site.

The investigator, or designee, must also explain to the subjects that they are completely free to refuse to enter the study or to withdraw from it at any time. Appropriate forms for documenting a signed and dated consent will be provided by either the investigator or by GSK CH.

The investigator, or designee, should sign and date each copy of the ICF to confirm that the consent process was completed correctly after the subject has signed.

The time the subject signed the informed consent form will also be captured on the Informed Consent Form as this is the point at which all Adverse Events and incidents will be captured from. The date and time of consent will be transcribed to the CRF.

If, during a subject's participation in the study, any new information becomes available that may affect the subject's willingness to participate in the study, each ongoing subject should receive a copy of this new information and be re-consented into the study. Each subject should be provided with a copy of the signed and dated amended consent form. The date of re-consent will be recorded on the CRF.

After signing the ICF, subjects will undergo the screening assessments to confirm that they meet all the inclusion criteria and none of the exclusion criteria. If the subject is confirmed eligible by the investigator (or designee) to participate in the study the subject is considered enrolled in the study.

### 8.1.1.2 Demographics

The following demographic information will be recorded in the CRF: year of birth, gender and race. Ethnicity and race of subjects will be recorded in accordance with FDA Guidance for Industry: Collection of Race and Ethnicity Data in Clinical Trials, 2005.

### 8.1.1.3 Medical History and Prior Medication/Treatment

Details of relevant medical and surgical history (in the last year), including allergies or drug sensitivity, will be documented in the CRF.

Prior medications/treatments, including prescription and non-prescription drugs, dietary supplements and herbal remedies, taken in the last 28 days and prior to signing the informed consent form, will be documented in the CRF.

The smoking/tobacco usage status of the subject should be recorded.

### 8.1.1.4 Dental History

The dental history of the subjects should be taken. Examples of the questions that should be solicited are given in [Appendix 15.3](#).

### 8.1.1.5 Inclusion/Exclusion Criteria

Inclusion and exclusion criteria information will be documented in the CRF. The OST, OHT, gross gingival assessment, well-made and well-fit assessments should be performed by suitably qualified examiners as described in [Section 5.8](#).

### 8.1.1.6 Subject Eligibility

The investigator and/or medically qualified designee will review inclusion/exclusion criteria, medical history, prior medications to confirm subject eligibility to participate in the clinical trial. This will be documented in the CRF.

To prepare for study participation, subjects will be instructed in the [Lifestyle Guidelines](#) and any [Concomitant Medication/Treatment\(s\)](#) requirements of the protocol.

## 8.2 Study Period

### 8.2.1 Visit 2/Day 0 – Baseline

Procedures will be conducted by the Investigator, or suitably qualified designee.

Subjects will undergo, in the following order (wherever possible), and findings documented in the CRF:

1. Changes in health, medication and non-drug treatments/procedures will be documented in the CRF.
2. Spontaneous reporting of adverse events and those elicited by asking subjects to respond to a non-leading question such as “How do you feel?” will be assessed.
3. Subject completes the questionnaire.
4. Subject removes RPD.
5. RPD is assessed for PDCI.

Property of GSK Consumer Healthcare - Confidential

May not be used, divulged, published or otherwise disclosed without the consent of GSKCH

SP1963/SOP-208661: Template Version: 14 Mar 2019

---

6. For a subset of subjects, photographic images of their RPD will be taken.
7. Subject undergoes a full OST examination.
8. Subject undergoes MGI assessment including a repeat assessment if required.
9. Subject undergoes a CI assessment.
10. Subject undergoes plaque disclosure and TPI including a repeat assessment if required.
11. Subject undergoes ODI assessment.
12. Subject undergoes BI assessment.
13. Review of the inclusion/exclusion criteria.
14. Subject eligibility assessed.
15. Subjects will be stratified and randomized to treatment group.
16. Subject's RPD will be cleaned by the study site and the subject will undergo a full sub and supra-gingival prophylaxis with confirmation of a TPI score of zero by a second suitably qualified member of site staff.
17. The subject's RPD will be returned.
18. Intervention group only - study products will be dispensed, including sundry items, product usage instructions and diary. Subject to perform supervised product usage and study staff to review instructions on correct product use with the subject for at home use.
19. No intervention group only – subject to receive only the diary.
20. All randomized subjects will receive standard oral care advice to brush their teeth twice per day with a fluoridated toothpaste, to remove their partial denture while sleeping, to clean their denture and to visit their dentist regularly.
21. AEs and incidents recorded.

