## Study Design

This will be a single-center, single-blind (to the examiner(s) performing the plaque, gingivitis, denture cleanliness and oral hygiene assessments), randomized, stratified (by denture material type and baseline mean overall MGI score), two-treatment, parallel group, 12 week clinical study in generally healthy, adult volunteers with one conventional RPD and generalized, mild-moderate, plaque-induced gingivitis (as determined by clinical examiner) and  $\geq 4$  natural teeth in each arch that meet all study criteria at both the Screening and Baseline visits (including  $\geq 30$  evaluable surfaces for clinical evaluation of gingivitis and plaque). The study will examine the effects of twice daily use of a range of dental/denture products (comprising use of a dentifrice, a mouthrinse and a denture cleanser) compared to no intervention (subjects who continue with their existing oral hygiene habits). There will be four visits to the study site: Screening, Baseline (when subjects are randomized), and after 6- and 12-Weeks use of the range of dental/denture products. Gingivitis will be assessed using the Modified Gingival Index (MGI) ([Lobene, 1986](#)) and a Bleeding Index (BI) ([Saxton and Ouderaa, 1989](#)). Plaque will be assessed by the Turesky modification of the Quigley & Hein Plaque Index (TPI) ([Lobene et al, 1982](#)). These indices are intended as markers of overall oral health. The cleanliness of the denture will be assessed by the examiner using the Partial Denture Cleanliness Index (PDCI) and overall oral hygiene will be assessed by the Oral Hygiene Index (OHI) ([Greene and Vermillion, 1960](#)). The subject's perception of denture/dental cleanliness will be determined through a questionnaire. Safety will be assessed through examination of the subject's oral hard and soft tissues throughout the study, recorded AEs and Incidents.

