**Table 1-1 Schedule of Activities**

| Procedure/Assessment  | Visit 1                      | Visit 2
Baseline
(Day 0)  | Visit 3
Week 6
(Day 42±3)  | Visit 4
Week 12
(Day 84±3)  |
|---|------------------------------|---|--|---|
|   | Screening
(Day -28 to -1) |   |  |   |
| Informed consent  | X                            |   |  |   |
| Demographics  | X                            |   |  |   |
| Medical history   | X                            |   |  |   |
| Current / concomitant medication  | X                            | X   | X  | X   |
| Dental history  | X                            |   |  |   |
| Well-fit assessment of RPD  | X                            |   |  |   |
| Collect used study products & diary   |                              |   | X  | X   |
| Compliance checks including diary review  |                              |   | X  | X   |
| Subject completes questionnaire   |                              | X   | X  | X   |
| Remove Removable Partial Denture (RPD)  | X                            | X   | X  | X   |
| Well-made assessment of RPD   | X                            |   |  |   |
| Partial denture cleanliness index (PDCI)  |                              | X   | X  | X   |
| Photography of RPDs representing the range of PDCI scores   |                              | X   | X                                | X                                 |
| Full oral soft tissue (OST) examination   | X                | X   | X  | X   |
| Full oral hard tissue (OHT) examination   | X                |   |  | X   |
| Gross gingival assessment   | X                            |   |  |   |
| Subject continuance   |                              |   | X  | X   |
| Modified Gingival Index (MGI) and Calculus Index (CI)   |                              | X   | X  | X   |
| Disclosing followed by Plaque Index (TPI), Oral Debris Index (ODI) and Bleeding Index (BI)   |                              | X   | X  | X   |
| Inclusion / exclusion criteria  | X                            | X   |  |   |
| Subject eligibility   | X                            | X   |  |   |
| Stratification / randomization  |                              | X   |  |   |
| Repeat MGI and TPI assessments    |                              | X   | X  | X   |

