| RPD cleansing and sub- & supra- gingival prophylaxis and flossing (with second clinician check after disclosing & residual plaque removal, if applicable i.e. confirmed plaque score of zero) |                              | X   |  |   |
| Return RPD to subject   | X                            | X   | X  | X   |

1 – 28 days between Visit 1 and Visit 2

|  |   |  |   |                 |                 |
|--|---|--|---|-----------------|-----------------|
| Dispense study products, toothbrush, product usage instructions, diary & timer   |   |  | X | X  |                 |
| Supervised subject brushing, mouth rinsing and denture cleansing at site including instruction in correct product usage  |   |  | X | X               |                 |
| Optional dental prophylaxis and RPD cleansing  |   |  |   |                 | X  |
| Adverse events / incidents   | X |  | X | X               | X               |
| Study conclusion   |   |  |   |                 | X               |

Abbreviations: OST = Oral Soft Tissue, OHT= Oral Hard Tissue, RPD = Removable Partial Denture, TPI= Turesky Plaque Index, BI= Bleeding Index, MGI= Modified Gingival Index, PDCI= partial denture cleanliness index, OHI= oral hygiene index, CI= calculus index, ODI= oral debris index.

Adverse Events (AEs) and therefore all Serious Adverse Events (SAEs) and medical device incidents will be collected immediately after a subject provides consent to participate in the study by the completion of the Informed Consent Form (ICF).

1. Subjects will abstain from overnight toothbrushing for a minimum of 12 hours (maximum of 18 hours) immediately prior to the assessment visits (Visits 2, 3 & 4).
2. Including smoking / tobacco-use status.
3. In relation to the general dentition exclusion criteria.
4. Timer and diary only dispensed once, at Visit 2 only. Subjects randomized to the no intervention group will receive only the diary. All randomized subjects to receive standard oral care advice.
5. Subjects will be instructed to brush their teeth using their normal dentifrice, use their existing denture cleansing procedure following their normal routine between screening and baseline visits.
6. For subjects randomized to the interventional group only.

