### **6.1.2 Preparation and Dispensing**

Subjects will be assigned to products in accordance with the randomization schedule generated by an approved GSK CH vendor, prior to the start of the study, using validated software.

Study product will be dispensed by qualified unblinded site personnel per the dosage/administration instructions. These staff members will not be involved in any safety, efficacy assessments or other aspects of the study that could be influenced by the knowledge of product a subject has been assigned to use. An additional member of the clinical site staff should ensure the dispensing procedures are completed accurately. Initial dispensing of study products should occur at Visit 2 with additional re-dispensing at Visit 3. The dispensing should be performed in a room away from other subjects and blinded study staff (especially the examiner performing the efficacy and safety assessments, who will be prevented from viewing subjects once they have their study products). The study site will be provided with opaque bags in which the study products, diaries and product usage instructions will be placed in the bag prior to the subject leaving the dispensing area. Subjects randomized to the no intervention group will have just their diaries in the opaque bag.

Subjects should be advised as to correct product usage in accordance with the [Product Usage Instructions](#) at each visit. All randomized subjects should receive standard oral care advice at Visit 2 (section 8.2.1).

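### Subjects are randomized before the baseline prophylaxis and denture cleaning, although allocation is not needed until dispensing; this leaves a small, cheaply closed opening for performance bias

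*Protocol*

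**What the plan says.** **Order.** Protocol 8.2.1 lists the Visit 2 procedures in sequence, to be followed where possible. Scoring and eligibility come first. Step 15 reads "Subjects will be stratified and randomized to treatment group". In step 16 the denture is cleaned by the site and "the subject will undergo a full sub and supra-gingival prophylaxis". The denture is returned at step 17, and products go to the intervention group at step 18. Section 4.1 describes the same sequence in prose.

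**Blind.** The Study Design paragraph of the protocol summary calls the trial "single-blind (to the examiner(s) performing the plaque, gingivitis, denture cleanliness and oral hygiene assessments". Section 6.5 is narrower: "This study is described as single-blind (to the examiner(s) performing the plaque and gingivitis assessments". Section 4.2 explains that subjects cannot be blinded, because the control group receives no product.

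**Safeguards.** Allocation is central, through an interactive system (6.5). Under 6.1.2 the unblinded dispensers may not take part in assessments or in "other aspects of the study that could be influenced by the knowledge of product a subject has been assigned to use". They work away from "blinded study staff (especially the examiner performing the efficacy and safety assessments", wording that reaches beyond the index examiner.

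**Cleaning end states.** Teeth are taken to TPI=0, with disclosure and a second clinician (4.1, 8.2.8). The denture is taken to PDCI 0 in 4.1, and to a plaque-free state judged by eye in 8.2.8.

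**The concern.** The cleaning is the common starting point of the trial. Section 4.2 expects the prophylaxis alone to improve gingivitis in the control group, and PDCI at Weeks 6 and 12 reflects what has built up on a denture cleaned at Visit 2. If the person cleaning knew the arm and worked more thoroughly in one than the other, the difference would carry into the between-arm comparison.

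The planned analysis could not remove it. SAP 3.1 takes baseline from the pre-treatment Visit 2 assessment, which 8.2.1 places before the cleaning. No score taken after the cleaning enters any model.

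Allocating before this step gains nothing that the documents mention, and it makes protection depend on who happens to know the result.

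**Working it through.** No figure in the plan bears on this point, so the check is a comparison of passages.

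**1. Is the allocation needed at step 15?**

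| Step in 8.2.1 | Content | Depends on arm? |
|---|---|---|
| 5–12 | PDCI, soft tissue examination, MGI, CI, TPI, ODI, BI | No |
| 13–14 | Criteria and eligibility | No |
| 15 | Stratify and randomize | – |
| 16 | Denture cleaning, prophylaxis, TPI=0 check | No |
| 17 | Denture returned | No |
| 18–19 | Products and diary, or diary only | Yes |

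The strata (5.4) are denture material, which is recorded in the dental history taken at screening, and baseline MGI, scored at step 8. Both are known before step 15 and neither is altered by step 16. Allocation could therefore follow the cleaning with the strata unchanged.

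**2. Who is protected from knowing the arm during step 16?**

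| Person | What the text gives |
|---|---|
| Dispensers | Unblinded, but kept out of influenceable tasks (6.1.2) |
| Second checker of the teeth | Called an examiner in 8.2.8 and confirms a plaque score, so plausibly inside the examiner blind |
| First prophylaxis clinician | Sections 5.8 and 8.2.6 set qualifications; no statement of blinding |
| Denture cleaner | Qualified clinical staff (4.1, 8.2.8); no statement of blinding |
| Subject | Open-label; no statement of when the arm is disclosed |

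**3. How far do the end states limit a difference?** For the teeth, the first clinician works to a visual and tactile standard with an explorer. Plaque is then disclosed, and a second clinician checks and removes what remains; 4.1 extends this to residual calculus. For the denture, 8.2.8 rules out a disclosing agent and neither section describes a second check. The denture cleaning is therefore the less protected of the two.

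**4. Could the ANCOVA adjust?** The models in SAP 4.4.1.2 (BI) and 4.5.1.6 (PDCI) use the baseline score as covariate, taken at step 12 and step 5 respectively. Both precede step 16, so neither carries information about how the cleaning was done.

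**5. Size.** For PDCI, suppose the share of dentures left at score 1 rather than 0 differed between arms by d. The Day 0 gap in mean PDCI would be 1 × d points on the 0–4 scale. The documents give no value for d, and none for how much of such a gap would last to Week 6 or 12. No estimate follows.

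**6. Side note on the denture end state.** In Table 9-1, scores 0 and 1 differ only in whether the probe picks up matter. Section 4.1 includes the probe criterion; 8.2.8 mentions only visual examination. Read alone, 8.2.8 would pass a denture at score 1. This wording applies to both arms alike and is independent of when randomization occurs.

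**The case against.** The strongest reply is that the blind already covers the cleaning. The dispensers are the only staff described as unblinded, and 6.1.2 keeps them from any task that knowledge of product could influence. Section 6.5 links the system's output to dispensing. The emergency procedure in 6.6 presupposes an investigator who does not know the arm. The second checker is an examiner confirming a plaque score. Much of this stands, and it is why disclosure is unlikely. It does not close the gap: blinding of the first clinician and the denture cleaner remains an inference. Section 6.5 also asks that the investigator's knowledge of allocation not affect enrolment, which points the other way, and nothing says when the subject learns the arm.

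It is also fair to say that 8.2.1 fixes its order only where possible. The listed default still randomizes first.

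Three stronger readings are tempting but unsupported.

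- A reader might infer that cleaning did or will differ by arm. No passage shows a cleaner learning the allocation.
- A reader might cite Table 1-1, where the row "Stratification / randomization" stands above "RPD cleansing and sub- & supra- gingival prophylaxis and flossing", as further proof of sequence. The rows are not chronological: the repeat MGI and TPI row also stands below randomization, although 8.2.1 places those repeats at steps 8 and 10. The order rests on 8.2.1 and 4.1 alone.
- A reader might translate the opening into an inflated type I error for the primary BI test. That needs an assumed bias which the documents do not supply, on the endpoint whose cleaning step is better checked.

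**Conclusion.** The point holds as a small, avoidable weakness in the design. Randomization precedes the cleaning by instruction, without need, and blinding during the cleaning is partly left to inference. The exposure is mainly to PDCI, a secondary endpoint. For BI it is smaller, given the explorer check, the disclosure and the second clinician.

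The size cannot be estimated and no bias is demonstrated. Any effect would require both that someone cleaning learned the arm and that the cleaning then differed within the stated end states. It is a worthwhile inexpensive improvement and does not challenge the primary result.

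The conflict between 4.1 and 8.2.8 on the denture end state is real, but it is a separate wording matter that falls equally on both arms.

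**What to change.** In Protocol 8.2.1 and 4.1, move stratification and randomization to after the prophylaxis, the TPI=0 check and the denture cleaning are complete, and before dispensing. This removes the route whoever is or is not blind. If the present order has to stay, the weaker alternative is a sentence in 6.5 stating that the prophylaxis clinician, the second checker and the denture cleaner are unaware of the allocation, and that neither they nor the subject receive the result before dispensing.

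The cost is a protocol amendment needing ethics approval before use (13.3.1), and an occasional subject who is cleaned but not then randomized. Sample size, strata, visits and analysis do not change.

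Separately, reconcile 4.1 and 8.2.8 so that a single stated method of confirming the denture end state applies to every denture in both arms.
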